**4.2. Exclusion Criteria**

To be enrolled in the study, potential subjects must meet **NONE** of the following exclusion criteria:

*Disease-Related*

1. Prior allogeneic Stem cell transplant within 6 months.
2. Active GVHD or concurrent treatment with immunosuppressive medications as prophylaxis for GVHD
3. Previous therapy with BTK inhibition
4. Known cerebral/meningeal disease
5. Nodular lymphocyte predominant Hodgkin's Lymphoma subtype

**PROTOCOL SPECIFIC**

### Concurrent Conditions

1. Concurrent therapy with other systemic anti-neoplastic or investigational agents
2. Patients with a known hypersensitivity to any excipient contained in the drug formulation
3. History of other malignancies, except:
  - Malignancy treated with curative intent and with no known active disease present for  $\geq 3$  years before the first dose of study drug and felt to be at low risk for recurrence by treating physician.
  - Adequately treated non-melanoma skin cancer or lentigo maligna without evidence of disease.
  - Adequately treated carcinoma in situ without evidence of disease.
4. Concurrent systemic immunosuppressant therapy (e.g., cyclosporine A, tacrolimus, etc., or chronic administration [ $>14$  days] of  $>20$  mg/day of prednisone) within 28 days of the first dose of study drug.
5. Vaccinated with live, attenuated vaccines within 4 weeks of first dose of study drug.
6. Recent infection requiring systemic treatment that was completed  $\leq 14$  days before the first dose of study drug.
7. Unresolved toxicities from prior anti-cancer therapy, defined as having not resolved to Common Terminology Criteria for Adverse Event (CTCAE, version 4), grade  $\leq 1$ , or to the levels dictated in the inclusion/exclusion criteria with the exception of alopecia.
8. Known bleeding disorders (e.g., von Willebrand's disease) or hemophilia.
9. History of stroke or intracranial hemorrhage within 6 months prior to enrollment.
10. Known history of human immunodeficiency virus (HIV) or active with hepatitis C virus (HCV) or hepatitis B virus (HBV). *Subjects who are positive for hepatitis B core antibody or hepatitis B surface antigen must have a negative polymerase chain reaction (PCR) result before enrollment. Those who are PCR positive will be excluded.*
11. Any uncontrolled active systemic infection.
12. Major surgery within 4 weeks of first dose of study drug.
13. Any life-threatening illness, medical condition, or organ system dysfunction that, in the investigator's opinion, could compromise the subject's safety or put the study outcomes at undue risk.
14. Currently active, clinically significant cardiovascular disease, such as uncontrolled arrhythmia or Class 3 or 4 congestive heart failure as defined by the New York Heart Association Functional Classification; or a history of myocardial infarction, unstable angina, or acute coronary syndrome within 6 months prior to randomization.
15. Unable to swallow capsules or malabsorption syndrome, disease significantly affecting gastrointestinal function, or resection of the stomach or small bowel, symptomatic inflammatory bowel disease or ulcerative colitis, or partial or complete bowel obstruction.
16. Concomitant use of warfarin or other Vitamin K antagonists.

17. Requires treatment with a strong cytochrome P450 (CYP) 3A4/5 inhibitor (see Appendix 3).
18. Currently active, clinically significant hepatic impairment Child-Pugh class B or C according to the Child Pugh classification (see Appendix 7).
19. Lactating or pregnant.
20. Unwilling or unable to participate in all required study evaluations and procedures.
21. Unable to understand the purpose and risks of the study and to provide a signed and dated informed consent form (ICF) and authorization to use protected health information (in accordance with national and local subject privacy regulations).

#### **4.3. Prohibitions and Restrictions**

Potential subjects must be willing and able to adhere to the following prohibitions and restrictions during the course of the study to be eligible for participation. During the study, subjects should avoid consuming food and beverages containing grapefruit or Seville oranges as these contain certain ingredients that inhibit CYP3A4/5 enzymes.

The following guidance should be applied during the perioperative period for subjects who require surgical intervention or an invasive procedure while receiving ibrutinib:

- For any surgery or invasive procedure requiring sutures or staples for closure, ibrutinib should be held at least 7 days prior to the intervention and should be held at least 7 days after the procedure, and restarted at the discretion of the investigator when the surgical site is reasonably healed without serosanguinous drainage or the need for drainage tubes.
- For minor procedures (such as a central line placement, needle biopsy, thoracentesis, or paracentesis) ibrutinib should be held for at least 3 days prior to the procedure and should not be restarted for at least 3 days after the procedure. For bone marrow biopsies that are performed while the subject is on ibrutinib, it is not necessary to hold ibrutinib for these procedures.
- For emergency procedures, ibrutinib should be held after the procedure until the surgical site is reasonably healed, for at least 7 days after the urgent surgical procedure.

### **5. TREATMENT OF SUBJECTS**

#### **5.1. Treatment Registration**

Consent must be signed before any study specific procedures are performed. Once a patient is consented, the site must email/fax a copy of the consent and the patient pre-registration form to the lead personnel at Karmanos Cancer Institute within 24 hours. Each patient will be assigned a unique identification number upon consenting and registration approval by the KCI lead coordinator which will be used to track all correlative shipments and study drug dispensation. The subject must also be entered into Oncore by the participating site within 24 hours of consent. Training for Oncore will be provided during site initiation. The participating site will provide

the registration form, eligibility checklist and all source documents to support patient eligibility to Karmanos and sites must receive approval from Karmanos prior to initiating study treatment. All subjects will receive the same treatment regimen, single-agent Ibrutinib.

### **5.1.1. Study treatment**

For the purposes of this study, ‘study drug’ refers to ibrutinib. Treatment will be administered until disease progression or relapse after CR, or occurrence of unacceptable toxicity, whichever comes first. Patients deriving benefit as deemed by the treating physician may continue on study drug until progression, or unacceptable toxicity.

### **5.2. Route and schedule**

Ibrutinib is to be taken in the morning (around the same time each day) with approximately 8 ounces (240 mL) of water. All 4 capsules should be taken at the same time. The capsules should be swallowed whole and should not be opened, broken, or chewed. The daily self-administered home treatment is to be continuous (without interruption). Subjects should avoid consuming food and beverages containing grapefruit or Seville oranges for the duration of the study due to CYP 3A4/5 inhibition. Subject should refrain from taking the study drug on the morning of study visits until seen at the site.

If a dose is missed, it can be taken as soon as possible on the same day with a return to the normal schedule the following day. The subject should not take extra capsules to make up the missed dose. Variations in dosing are not considered unsafe if more than 12 hrs of time are provided between doses. If doses occur within 12 hours of each other this will be considered a minor deviation. During the first 15 months, study drug will be dispensed at the beginning of each 28-day cycle. Subjects will be provided with 2 days coverage each time study drug is dispensed to allow for delayed return visits. Unused ibrutinib, dispensed during previous visits, must be returned and drug accountability records updated. Returned capsules must be discarded and cannot be re-used in this study or outside the study. Study staff will instruct subjects on how to store ibrutinib for at-home use as indicated for this protocol. After 15 months of treatment, patient site visits may be conducted every 56 days. Sufficient drug supply until next visit will be dispensed.

### **5.3. Study Medication**

Subjects will receive 560 mg oral ibrutinib once per day, continuously during a 28 day treatment cycle. Each capsule contains 140 mg of ibrutinib. Subjects will be instructed to take 4 capsules for a dose of 560 mg.

### 5.3.1. Ibrutinib

#### 5.3.1.1. Formulation/Packaging/Storage

Ibrutinib capsules are provided as a hard gelatin capsule containing 140 mg of ibrutinib. All formulation excipients are compendial and are commonly used in oral formulations. Refer to the ibrutinib Investigator's Brochure for a list of excipients.

The ibrutinib capsules will be packaged in opaque high-density polyethylene plastic bottles with labels bearing the appropriate label text as required by governing regulatory agencies. All study drugs will be dispensed in child-resistant packaging. Study drug labels will contain information to meet the applicable regulatory requirements.

**Drug Storage:** The labeled storage condition for ibrutinib is between 15-25°C (59-77°F), with excursions permitted up to 30°C. Total cumulative excursions between 25°C and 30°C must not exceed 12 months. Temperatures lower than 15°C or greater than 30°C must be reported to Pharmacyclics for evaluation of impact on product quality. In storage areas where the temperature can exceed or fall below the required storage conditions (e.g., air conditioning, heating), measures must be in place to maintain the required temperature. Ibrutinib should be kept away from direct sunlight.

Temperature conditions during on-site storage of study drug must be closely monitored and recorded (e.g., temperature logs, or data, charts or graphs from temperature monitoring equipment or devices). All monitoring equipment must be calibrated in accordance with the manufacturer's recommendations. All documentation/data of the storage temperature must be retained in accordance with the records retention policy outlined in the Protocol and applicable legal and regulatory requirements.

The storage temperature documentation must identify or link to (e.g., through the serial number or unique identifier) the thermometer or temperature monitoring equipment and, if applicable the refrigerator/freezer. These logs must be made available to the monitors for review at routine interim monitoring visits.

#### 5.3.1.2. Dose and Administration

Ibrutinib 560 mg (4 x 140-mg capsules) is administered orally once daily. The capsules are to be taken around the same time each day with 8 ounces (approximately 240 mL) of water. The capsules should be swallowed intact and subjects should not attempt to open capsules or dissolve them in water. The use of strong CYP3A inhibitors/inducers, and grapefruit and Seville oranges should be avoided for the duration of the study (**Appendix 3**).

If a dose is not taken at the scheduled time, it can be taken as soon as possible on the same day with a return to the normal schedule the following day. The subject should not take extra capsules to make up the missed dose.

The first dose will be delivered in the clinic on Day 1, after which subsequent dosing is typically on an outpatient basis. Ibrutinib will be dispensed to subjects in bottles at each visit. Unused ibrutinib dispensed during previous visits must be returned to the site and drug accountability records (Section 5.4.1.3) updated at each visit. Returned capsules must not be re-dispensed to anyone.

### **5.3.1.3. Drug Accountability**

The site specific investigator is responsible for ensuring that all study drug received at the site is inventoried and accounted for throughout the study. The dispensing of study drug to the subject, and the return of study drug from the subject (if applicable), must be documented on the drug accountability form. The subject or their legally acceptable representatives where applicable, must be instructed to return all original containers, whether empty or containing study drug. All study drug will be stored and disposed of per institution's protocol. Site staff must not combine contents of the study drug containers. Study drug must be handled in strict accordance with the protocol and the container label, and must be stored at the study site in a limited-access area or in a locked cabinet under appropriate environmental conditions. Unused study drug, and study drug returned by the subject, must be available for verification by the lead investigators. When study drug supplies are destroyed on site per institutional protocol, a tablet count and disposal method should be documented on the drug return form. Study drug should be dispensed under the supervision of the investigator or a qualified member of the investigational staff, or by a hospital/clinic pharmacist. Study drug will be supplied only to subjects participating in the study. Returned study drug (ibrutinib) must not be dispensed again, even to the same subject. Study drug may not be relabeled or reassigned for use by other subjects. The investigator agrees neither to dispense the study drug from, nor store it at, any site other than the study sites agreed upon with the investigating sponsor.

The investigator will be provided with a drug accountability diary to be provided to patients beginning therapy prior to or on day one of treatment. Patients must be instructed to document ibrutinib usage per the diary requirements. The drug diary should be reviewed by the study staff prior to drug dispensation for every cycle. Discrepancies between the returned drug accountability and diary must be evaluated at the beginning of each cycle.

### **5.3.1.4. Overdose**

There is no specific experience in the management of ibrutinib overdose in patients. No maximum tolerated dose (MTD) was reached in the Phase 1 study in which subjects received up to 12.5 mg/kg/day (1400 mg/day). Healthy subjects were exposed up to single dose of 1680 mg. One healthy subject experienced reversible Grade 4 hepatic enzyme increases (AST and ALT) after a dose of 1680 mg. Subjects who ingest more than the recommended dosage should be closely monitored and given appropriate supportive treatment. Refer to Section 10 for further information regarding AE reporting.

### 5.3.1.5. Dose Modification for Adverse Reactions

The dose of study drug should be modified according to the dose modification guidelines in Table 1 if any of the following toxicities occur:

- Grade 4 ANC (<500/ $\mu$ L) for more than 7 days. See Section 6 for instructions regarding the use of growth factor support.
- Grade 3 thrombocytopenia (<50,000/ $\mu$ L) in the presence of clinically significant bleeding events.
- Grade 4 thrombocytopenia (<25,000/ $\mu$ L).
- Grade 3 or 4 nausea, vomiting, or diarrhea if persistent, despite optimal anti-emetic and/or anti-diarrheal therapy.
- Any other Grade 4 or unmanageable Grade 3 toxicity.

For Grade 3 or 4 atrial fibrillation or persistent atrial fibrillation of any grade, consider the risks and benefits of ibrutinib treatment. If clinically indicated, the use of anticoagulants or antiplatelet agents may be considered for the thromboprophylaxis of atrial fibrillation (Section 6.2.4).

Table 1. Ibrutinib Dose Modifications

Occurrence	Action to be Taken
First	Withhold study drug until recovery to Grade $\leq$ 1 or baseline; may restart at original dose level
Second	Withhold study drug until recovery to Grade $\leq$ 1 or baseline; may restart at 1 dose level lower (i.e. 420 mg/day for 560 mg /day dose )
Third	Withhold study drug until recovery to Grade $\leq$ 1 or baseline; may restart at 1 dose level lower (i.e. 280 mg/day for 420 mg /day dose )
Fourth	Discontinue study drug

*A high number of circulating malignant cells (>400,000/ $\mu$ L) may confer increased risk of leukostasis; these subjects should be closely monitored. Administer supportive care such as hydration and/or leukaphoresis as indicated. Ibrutinib may be temporarily held, and principal investigator should be contacted.*

### 5.4. Dose Modification for Hepatic Impaired Subjects

Ibrutinib is metabolized in the liver and therefore subjects with clinically significant chronic hepatic impairment at the time of screening (Child- Pugh class C) are excluded from study participation. Concomitant use of strong CYP inhibitors is not permitted in subjects with chronic hepatic impairment. Refer to Appendix D for Child-Pugh classification. Please refer to Table 2

for dose modifications due to hepatic impairment. Monitor subjects for signs of toxicity and follow dose modification guidance as needed (Refer to Appendix 7).

Table 2: Dose Modification due to Hepatic Impairment

	Child Pugh class A (Mild hepatic impairment)*		Child Pugh Class B (Moderate hepatic impairment)**		Child Pugh class C (Severe hepatic impairment)
	Ongoing at time of enrollment	Develops during study	Ongoing at time of enrollment	Develops during study	Develops during study
Ibrutinib Dose (daily)	280 mg	280mg	140 mg	140 mg	Hold until improves to moderate [Class B] or better)

\* If further reduction is needed due to non-hepatic toxicity, dose may be reduced to 140 mg. In the event that additional reduction is needed, ibrutinib should be held for non-hepatic toxicity until resolution.

\*\* If further reduction is needed due to non-hepatic toxicity, ibrutinib should be held until resolution.

## 5.5. Criteria for Permanent Discontinuation of Study Drug

Study drug may be held for a maximum of 28 consecutive days. Study treatment should be permanently discontinued in the event of a toxicity lasting >28 days. Once the ibrutinib dose is reduced it cannot be re-escalated without a discussion with the medical monitors ([name] or [name]).

## 6. CONCOMITANT MEDICATIONS/PROCEDURES

### 6.1. Permitted Concomitant Medications

Supportive medications in accordance with standard practice (such as for emesis, diarrhea, etc.) are permitted. Use of neutrophil growth factors (filgrastim and pegfilgrastim) or red blood cell growth factors (erythropoietin) is permitted per institutional policy and in accordance with the ASCO guidelines (Smith 2006) beginning cycle two day one of therapy. Transfusions may be given in accordance with institutional policy.

Short courses ( $\leq$ 14 days) of steroid treatment for non-cancer related medical reasons (e.g., joint inflammation, asthma exacerbation, rash, antiemetic use and infusion reactions) at doses that do not exceed 100mg per day of prednisone or equivalent are permitted.

Treatment for autoimmune cytopenias are permitted for <14 days at doses that do not exceed 100 mg per day of prednisone or equivalent.

Standard supportive care therapies (e.g., antiemetics, loperamide) needed for the management of symptoms are permitted, as clinically indicated, other than anticancer treatment.

## 6.2. Medications to be Used with Caution

### 6.2.1. CYP3A- Inhibitors/Inducers

Ibrutinib is metabolized primarily by CYP3A4. Concomitant use of ibrutinib with drugs that strongly or moderately inhibit CYP3A can increase ibrutinib exposure. Dose adjustment of ibrutinib due to concomitant use of CYP3A inhibitors should follow Table 3.

Table 3. Dose Modification Guidance for CYP3A Inhibitors/Inducers

Patient Population	Co-administered Drug	Recommended Ibrutinib Dose for the Duration of the Inhibitor Use a
B-Cell Malignancies	Mild CYP3A inhibitors	420 mg or 560 mg once daily per indication. No dose adjustment required.
	Moderate CYP3A inhibitors	280 mg once daily.
	Voriconazole Posaconazole at doses less than or equal to suspension 200 mg BID	140 mg once daily.
	Other strong CYP3A inhibitors Posaconazole at higher doses b	Avoid concomitant use and consider alternative with less CYP3A inhibitory potential. If these inhibitors will be used short-term (such as anti-infectives for seven days or less), interrupt ibrutinib. If the benefit outweighs the risk, and long-term dosing with a CYP3A inhibitor is required (more than seven days), reduce ibrutinib dose to 140 mg once daily for the duration of the inhibitor use.

a. Monitor for adverse reactions to IMBRUVICA and interrupt or modify dose as recommended (see Dosage and Administration).

b. Posaconazole at higher doses (posaconazole suspension 200 mg three times daily or 400 mg twice daily, posaconazole IV injection 300 mg once daily, posaconazole delayed-release tablets 300 mg once daily).

After discontinuation of a CYP3A inhibitor, resume previous dose of ibrutinib.

Avoid concomitant use of systemic CYP3A inducers (eg, carbamazepine, rifampin, phenytoin, and St. John's Wort). Consider alternative agents with less CYP3A induction.

A list of common CYP3A inhibitors and inducers is provided in Appendix 3. A comprehensive list of inhibitors, inducers, and substrates may be found at

<http://medicine.iupui.edu/clinpharm/ddis/main-table/>. This website is continually revised and should be checked frequently for updates.

For the most comprehensive effect of CYP3A inhibitors or inducers on ibrutinib exposure, please refer to the current version of the IB.

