## Appendix 3. Inhibitors and Inducers of CYP3A

Inhibitors of CYP3A are defined as follows. A comprehensive list of inhibitors can be found at the following website: <http://medicine.iupui.edu/clinpharm/ddis/table.aspx>. The general categorization into strong, moderate, and weak inhibitors according to the website is displayed below. Refer to [Section 6.2.1](#) on instructions for concomitant use of CYP3A inhibitors and inducers with ibrutinib.

Inhibitors of CYP3A	Inducers of CYP3A
Strong inhibitors:	
INDINAVIR	Carbamazepine
NELFINAVIR	Efavirenz
RITONAVIR	Nevirapine
CLARITHROMYCIN	Barbiturates
ITRACONAZOLE	Glucocorticoids
KETOCONAZOLE	Modafinil
NEFAZODONE	Oxcarbazepine
SAQUINAVIR	Phenobarbital
SUBOXONE	Phenytoin
TELITHROMYCIN	Pioglitazone
Moderate inhibitors:	Rifabutin
Aprepitant	Rifampin
Erythromycin	St. John's Wort
diltiazem	Troglitazone
Fluconazole	
grapefruit juice	
Seville orange juice	
Verapamil	
Weak inhibitors:	
Cimetidine	
All other inhibitors:	
Amiodarone	
NOT azithromycin	
Chloramphenicol	
Boceprevir	
Ciprofloxacin	
Delavirdine	
diethyl-dithiocarbamate	
Fluvoxamine	
Gestodene	
Imatinib	
Mibepradil	
Mifepristone	
Norfloxacin	
Norfluoxetine	
star fruit	
Telaprevir	
Troleandomycin	
Voriconazole	

Source: <http://medicine.iupui.edu/clinpharm/ddis/table.aspx>.

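### Appendix 3 does not list voriconazole or posaconazole as strong CYP3A inhibitors, although Table 3 treats both as strong, so exclusion 17 and the section 5.4 prohibition can fail to apply to them

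*Combined protocol and SAP*

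**What the plan says.** Section 6.2.1 ties the dose to inhibitor strength: "Dose adjustment of ibrutinib due to concomitant use of CYP3A inhibitors should follow Table 3". Table 3 then has four rows:

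- mild inhibitors: no change
- moderate inhibitors: 280 mg
- "Voriconazole Posaconazole at doses less than or equal to suspension 200 mg BID": 140 mg
- "Other strong CYP3A inhibitors Posaconazole at higher doses": avoid if possible, interrupt ibrutinib for short courses, or give 140 mg if long-term use is unavoidable

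For the drugs in each class, section 6.2.1 points to Appendix 3, with a website and the Investigator's Brochure as wider sources. Appendix 3 introduces its table with "The general categorization into strong, moderate, and weak inhibitors according to the website is displayed below". The table nevertheless has a fourth heading, "All other inhibitors", which carries no strength. Voriconazole is under it. Posaconazole does not appear in Appendix 3.

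Three rules turn on whether a drug is strong:

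- Exclusion 17 (section 4.2) bars a subject who meets "Requires treatment with a strong cytochrome P450 (CYP) 3A4/5 inhibitor (see Appendix 3" (the Synopsis has the same criterion and the same pointer).
- Section 5.3.1.2 says "The use of strong CYP3A inhibitors/inducers, and grapefruit and Seville oranges should be avoided for the duration of the study" and also cites Appendix 3.
- Section 5.4 says "Concomitant use of strong CYP inhibitors is not permitted in subjects with chronic hepatic impairment".

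**The concern.** An exclusion criterion and a safety prohibition both depend on one word, and the list cited to define that word disagrees with the dosing table. Anyone who checks exclusion 17 against Appendix 3, as the criterion instructs, will not find either azole among the strong inhibitors. Anyone who works from Table 3 will conclude that both are strong.

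The matter at stake is safety and eligibility. Section 6.2.1 states that strong and moderate inhibitors can raise ibrutinib exposure. Section 1.4.1 reports a 2.7-fold increase in AUC with Child-Pugh class A impairment compared with normal liver function, before any inhibitor is added. Class A subjects can enrol, since exclusion 18 bars only classes B and C, and Table 2 gives class A a dose at enrolment. They are therefore the subjects for whom the section 5.4 ban matters most.

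Use of an azole is foreseeable: Table 3 names these drugs, and section 1.5.1 advises considering prophylaxis in subjects at raised risk of opportunistic infection.

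**Working it through.** The plan states no figure on this point, so the check is a comparison of texts plus a count.

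**Step 1. Strength of the two drugs in each place.**

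| Place | Voriconazole | Posaconazole |
|---|---|---|
| Table 3 | Own row at 140 mg; the next row covers the *other* strong inhibitors, so strong by implication | Lower doses share the voriconazole row; higher doses share the row of other strong inhibitors |
| Appendix 3 | Listed with no strength | Not listed |

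**Step 2. What each rule then gives.**

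| Rule | Using Appendix 3 as printed | Using Table 3's class |
|---|---|---|
| Exclusion 17, drug required at entry | Not triggered | Excluded |
| Section 5.3.1.2, avoid strong inhibitors | Not triggered | Avoid |
| Section 5.4, chronic hepatic impairment | Not triggered | Prohibited |
| On-study dose, no hepatic impairment | Table 3 row applies by drug name | Same |

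Section 5.4 does not itself cite Appendix 3, but Appendix 3 is the only list by strength in the protocol. The last row shows that the on-study dose is not in doubt: voriconazole is named in Table 3, at 140 mg. The discrepancy is one of class, and it reaches whatever depends on class.

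**Step 3. Interaction with the Table 3 wording.** If both drugs are simply moved to the strong list, section 5.3.1.2 would say to avoid them throughout, while Table 3 gives 140 mg for voriconazole and lower-dose posaconazole with no instruction to avoid. Re-filing alone therefore leaves a second inconsistency, and the correction must include a sentence in 5.3.1.2.

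**Step 4. Count of Appendix 3 inhibitors.** The line that says azithromycin is *not* an inhibitor is left out.

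- Strong 10 + moderate 7 + weak 1 + unclassed 17 = 35.
- Unclassed: 17/35 = 48.6%.
- Voriconazole is the only one of the 17 named in Table 3, so 17 − 1 = 16 match no Table 3 row: 16/35 = 45.7%.

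This takes Table 3's mild class to be Appendix 3's weak class.

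**Step 5. Effect on the design.** With n = 31 and rejection at 13 or more responses, the exact binomial tail is 0.1069 at a response rate of 30% and 0.859 at 50%. These match the plan's 10.69% and 85%. No input to them involves CYP3A inhibitors.

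**The case against.** The strongest reply has four parts.

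1. *The conflict is only implied.* Table 3 never says outright that voriconazole is strong, and Appendix 3 does not say that it is not. That is true. But an exclusion criterion should not have to be inferred from the word *other* in a dosing table, and the list it cites gives no answer for voriconazole or posaconazole.

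2. *Other sources fill the gap.* Section 6.2.1 calls Appendix 3 a list of common inhibitors and adds a website and the Investigator's Brochure, neither of which is in the documents. For the 16 other unclassed drugs this reply largely stands. A reader might infer that they have no dose at all, but the documents show only that none is printed in the protocol. The reply is weaker for the two azoles, because exclusion 17 cites Appendix 3, and Appendix 3 says that its classes already come from the website.

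3. *Entry is controlled centrally.* Section 5.1 requires each site to send the eligibility checklist and source documents to the lead institution and to wait for approval before treatment. A reader might infer that the 4 institutions would reach different eligibility decisions, and this procedure is why the documents do not support that. It does not remove the defect, since the central check would use the same criterion and the same list.

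4. *Few subjects are likely to be affected.* Exclusions 6 and 11 already remove those with recently treated or uncontrolled infection, which leaves mainly prophylaxis at entry, and section 1.5.1 names no prophylactic drug. This limits how often the problem would arise. The section 5.4 ban still matters for azoles started on study.

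**Conclusion.** The mismatch is real and confined to two named drugs. As printed, Appendix 3 does not trigger exclusion 17 for a subject who requires voriconazole or posaconazole, and it gives no trigger for the section 5.4 prohibition. Table 3's class would trigger both. The conclusion assumes that *other strong* in Table 3 means that the drugs in the row above are strong, and that the Appendix 3 headings apply as they appear in the text. How many subjects would be affected cannot be estimated from the documents.

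Two stronger readings are not supported:

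- A reader might infer that a subject on voriconazole at 140 mg is under-treated, at a quarter of the nominal dose, and so distorts the response rate. The Table 3 reduction is an adjustment for raised exposure. Nothing in the documents shows that such a subject is under-exposed, and no frequency is given from which to size an effect on the response rate.
- A reader might object that the flat 280 mg for a moderate inhibitor is no reduction for someone already at 280 mg. The documents do not show that dose to be unsafe there.

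The point is an inconsistency in a safety and eligibility rule. It does not threaten the primary analysis, but it is worth correcting because the remedy is small.

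**What to change.** **Main change.** In Appendix 3, list voriconazole and posaconazole (all doses) under the strong inhibitors. In section 5.3.1.2, add a sentence such as: *If voriconazole or posaconazole becomes necessary during the study, the Table 3 instruction applies, except in subjects with chronic hepatic impairment, in whom section 5.4 prohibits its use.* Exclusion 17, 5.3.1.2, 5.4 and Table 3 then agree.

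**Secondary tidy-up.** Place each of the other 16 unclassed inhibitors under strong, moderate or weak. For any that cannot be placed, require contact with the medical monitor before the ibrutinib dose is set. A default of 280 mg should not be used. It has no basis in the documents, would be twice Table 3's 140 mg if the drug proved strong (280/140 = 2), and would halve the 560 mg dose needlessly if it proved weak (280/560 = 0.5).

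**Cost.** A protocol amendment that re-sorts one appendix table and adds one sentence to 5.3.1.2 and a short medical-monitor instruction. Sample size, visits and analysis do not change.
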